
- Inclusion of requirements for all NHL subjects in Part 2 to have local p53 mutational analysis done and results available prior to dosing in the trial unless the subject's tumor has previously been demonstrated to harbor a p53 mutation. If p53 status was not determined, an archival sample or a fresh biopsy must be provided (Section 8.2.1).
- In case one NHL cohort reaches futility at any Interim Analysis, further enrolment into the other NHL cohort will require central confirmation (Section 8.2.1).

Part 3:

- Inclusion of collection of local and central PD-L1 test results (Section 8.7.2).
- Clarification of Pembrolizumab contraceptive requirements for females of reproductive potential (Section 4.9.1).
- Inclusion of cervical cancer patients as additional population for enrolment into the Dose Escalation cohort and relevant changes in the inclusion criteria (Section 5.1).
- Inclusion of language to allow for over-recruitment of 1 patient in Part 3 along with updates to the safety stopping rules for dose escalation decisions within Part 3 (Section 4.4.4). Operating characteristics for Part 3 in the event of over-recruitment were added in Section 11.10.4.7.

- Addition of requirement to replace any subject who fails to receive 80% of planned doses in Part 3 due to reasons other than toxicity (Section 4.4.4).
- Administrative change with regards to change in name of Programme Physician lead name.

TMF-11799334	17-FEB-21	Amendment No. 7
CCI		

This protocol amendment also serves to include additional safety assessments, reduce the total blood volume drawn per subject and to update the HIV/HCV, HBV exclusion criteria. As such, ophthalmic evaluations, Folate/B12 vitamin testing and clarifications for thyroid function testing have been added and the updated SoAs are applicable to all ongoing subjects.

The following changes have been made (in addition to the correction of minor typographical and formatting errors):

Study Population

- An error has been corrected in Exclusion Criterion 9 to specify the exclusion of subjects with a CD4 count ≥350 cells/uL rather than >300 cells/uL.
- Exclusion Criteria has been updated to specify that subjects with HBV infection may participate in the study provided they are on a suppressive antiviral therapy prior to initiation of cancer therapy.
- An exclusion criterion has been added to exclude patients with a history of optic nerve neuropathy or neuritis.

Part 1:

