8.2.1. Critical Baseline Assessments

The following are required at baseline:

- Imaging/efficacy:
 - Part 1: All subjects should undergo contrast-enhanced CT of the chest, abdomen, and pelvis (and/or other areas as indicated by the subject's underlying disease) as well as an MRI of the brain.

NOTE: Although CT scan is preferred, MRI may be used as an alternative method of baseline disease assessment for abdomen/pelvis, especially for those subjects where a CT scan is contraindicated due to allergy to contrast, provided that the method used to document baseline status is used consistently throughout study treatment to facilitate direct comparison. An unenhanced CT of the chest

can replace the enhanced CT of the chest, but MRI of the chest is not recommended.

- Part 2, solid tumor cohorts, and Part 3: All subjects should undergo contrastenhanced CT of the chest, abdomen, and pelvis (and/or other areas as indicated by the subject's underlying disease) as well as an MRI of the brain. If MRI of the brain is contraindicated, then an equivalent scan (e.g., contrast-enhanced CT of the brain) may be performed instead.
- Part 2, GBM cohort: All subjects should undergo MRI of the brain. Refer to the Imaging Acquisition Guidelines (IAG) for scanning guidelines
- Part 2, NHL cohorts: All baseline (and subsequent) scanning should be performed as clinically indicated based on the NHL subtype and the manifestation of the subject's disease. For subjects with measurable tumors, contrast-enhanced CT of the neck, chest, abdomen, and pelvis should be performed. If PET/CT is used to assess disease, the CT component must be performed to diagnostic quality (including the required anatomical coverage and use of IV and oral contrast). Other modalities (e.g., medical photography for cutaneous T-cell lymphoma (TCL) or bone marrow biopsy) may be used after discussion with the medical monitor.
- Disease characteristics (as available):
 - The results of any mutational analysis of tumor or other associated tissue (e.g., cytology, circulating tumor cells, cf-DNA), including p53 status (if available).
 - For Part 2 NHL p53 status and NSCLC p53 WT status is required prior to dosing
 - The size(s) and location(s) of target lesion(s) used for response characterization for at least two prior lines of therapy, as well as a description of the dates of service and changes made to management
- Tumor biopsies:

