 - All subjects in Part 1 (dose escalation and, the PK/PD/biomarker/metabolite cohort/s), as well as all subjects in Parts 2 and 3, must submit an archival tumor specimen in addition to any fresh biopsies required in individual cohorts (see below). The archival specimen will be used for retrospective testing for potential markers of sensitivity and/or resistance (e.g., p53). If archival specimen is not available, a fresh biopsy must be performed. Further details regarding processing will be provided in the SRM.
 - NOTE: All NHL subjects in Part 2 must have a local p53 mutational analysis result prior to dosing unless the subject's tumor has previously been demonstrated to harbor a p53 mutation. If local p53 status was not determined, analysis may be performed on archival tissue, but if archival tissue is not available, a fresh biopsy must be performed. NHL subjects with neither archival tumor sample nor accessible tumor for fresh biopsy will not be permitted to enroll. Further details will be provided in the SRM. The intent is to accrue 10 subjects each of WT and mutant p53. As the sub-cohorts are filled, it may become necessary to delay enrollment until p53 status is formally designated. In case one NHL cohort reaches futility at any Interim Analysis, further enrolment

into the other NHL cohort will require central confirmation. NOTE: All NSCLC subjects in Part 2 must have a local genomic p53 mutational analysis result prior to dosing. If local p53 status was not determined, an archival sample or a fresh biopsy must be provided.

- Individual subjects in the dose escalation portion of Part 1 may be required to provide paired biopsies for PD evaluation as described in Section 4.2.5 and Section 8.6.2. For these subjects, a fresh baseline tumor biopsy is required and should be obtained within 14 days of the first dose of GSK3326595. Further details will be provided in the SRM.
- In the Part 1 PD/biomarker/metabolite expansion cohort(s), a fresh baseline tumor biopsy is required from all subjects and should be obtained within 14 days prior to the first dose of GSK3326595. Further details will be provided in the SRM.

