2.4. Statistical Hypotheses

In Part 1, the primary endpoints of this study are safety and tolerability; the MTD and RP2D will also be determined. No formal statistical hypotheses will be tested. The primary focus will be on determining the recommended dose for further exploration, the safety profile, and the PK of GSK3326595 in subjects with advanced solid malignancies. Analyses will be descriptive and exploratory.

The primary goal of Part 2 is to evaluate disease-specific clinical activity in subjects with select solid tumors and NHL. The cohorts will be terminated for futility based on interim analysis described in Section 3.1

- For TNBC and ER+BC, efficacy is defined as a clinically meaningful response rate (defined as the percentage of subjects that have achieved a CR or PR) of 25% relative to a 10% historical control response rate.
- For mTCC, efficacy is defined as a clinically meaningful response rate (defined as the percentage of subjects that have achieved a CR or PR) of 30% relative to a 15% historical control response rate.
- For recurrent GBM, efficacy is defined as a clinically meaningful improvement in the rate of subjects who remain progression-free at six months (defined as a 35% six-month PFS rate relative to a 17% historical six-month PFS rate).
- For ACC and HPV-positive solid tumors, efficacy is defined as a clinically meaningful response rate (defined as the percentage of subjects that have achieved a CR or PR) of 30% relative to a 10% historical control response rate.
- For NHL (p53 wild-type, p53 mutant, and p53 unknown cohorts), efficacy is defined as a clinically meaningful response rate (defined as the percentage of subjects that have achieved a CR or PR) of 30% relative to a 10% historical control response rate.
- For NSCLC, efficacy is defined as a clinically meaningful response rate (defined as the percentage of subjects that have achieved a CR or PR) of 30% relative to a 10% historical control response rate. An interim futility analysis will be used to determine the scope of further development in this cohort.

The primary goal of Part 3 is to evaluate the safety and tolerability of GSK3326595 in

combination with pembrolizumab in solid tumors. No formal statistical hypotheses will be tested.

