To further investigate clinical activity across the pre-specified cohorts, an adaptive design utilizing a Bayesian hierarchical model will be employed for the mTCC, TNBC, p53 WT NHL and p53 mutant NHL cohorts in Part 2. [Berry, 2013; Escobar, 1995; Neal, 2000; Sethuraman, 1994] Multiple interim evaluations of the accumulating data to determine if one or more cohorts should discontinue enrollment early due to futility will be incorporated. Interim and final evaluations will be based on a hierarchical model that borrows information in a limited way from cohorts that demonstrate similar treatment effects based on the accumulated trial data. Traditional estimates based on independent analyses will also be provided. π_j is the true response rate for cohort *j*, where j = 1, ..., 4 and indexes the four cohorts. C_j is the historical control response rate for the jth cohort. The historical controls vary by cohort and are provided in Section 2.4. The study is powered to detect a high clinically meaningful response rate and is based on the cohort model assessment of whether there is sufficiently high probability that π_j exceeds C_j. The posterior probability that the ORR for a given cohort is greater than C_j will be computed according to the following comparison:

 $P \; (\pi_j \geq C_j \mid \text{current data}) \; \text{for the j-th cohort}$

If this posterior probability is sufficiently low within a given cohort, then this will provide insufficient evidence to suggest that the ORR is greater than its respective historical control. Conversely, if a sufficiently high posterior probability is observed, this will provide evidence that the ORR is greater than the historical control, and the dose will be declared efficacious in that cohort. Thresholds for decision making are defined in the protocol.

Full details regarding the hierarchical modeling framework are described in the protocol at Appendix 11.

3.1.3. Interim Analysis for Part 1 Cohorts and for ACC Cohort in Part 1 and Part 2

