- Part 2 ACC 400mg QD Capsule Cohort
- Part 2 ACC 300mg QD Tablet Cohort
- Part 2 NHL P53 Mutant 400 mg QD Capsule
- Part 2 NHL P53 Mutant 300 mg QD Capsule
- Part 2 NHL P53 Mutant 300 mg QD Tablet (if applicable)
- Part 2 NHL P53 Wild Type 400 mg QD Capsule
- Part 2 NHL P53 Wild Type 300 mg QD Capsule
- Part 2 NHL P53 Wild Type 300 mg QD Tablet (if applicable)
- Part 2 NHL P53 Unknown 400 mg QD Capsule
- Part 2 NHL P53 Unknown 300 mg QD Capsule
- Part 2 NHL P53 Unknown 300 mg QD Tablet (if applicable)
- Part 2 NSCLC 300 mg QD Capsule
- Part 2 NSCLC 300 mg QD Tablet (if applicable)
- Part 2 ACC TN 300mg Tablet Cohort

NB 1: NHL P53 status is based on central lab data. If the central lab data is missing then the status will be considered Unknown.

NB 2: As per GSK communication, as of *3Nov2021 tablet and capsule cohorts within the same disease/dosage groups will be combined.*

For Part 3 combination dose escalation, some AE and exposure tables and listings will be displayed for GSK3326595 and pembrolizumab separately. All others will be summarized and listed by dose levels of both GSK3326595 plus pembrolizumab. (e.g., GSK3326595 100mg + pembrolizumab).

Subjects enrolled in Part 1, may be included in a Part 2 disease-specific cohort analyses (tables and figures) if the subjects were treated at the Part 2 dose expansion and have the same disease type as required for the cohort. These subjects will be provided in a separate listing as well. Additional safety tables, may be provided for all subjects treated at the RP2D, regardless of the Part of the study to which they were enrolled.

Unless otherwise noted, the denominator for the percentage is the number of subjects in the analysis population used for that summary.

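### NHL p53 status is taken from central results alone, and the resulting Unknown group has an efficacy criterion but no stated place in the four-cohort model

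*SAP*

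**What the plan says.** **Status rule.** SAP 5.1.1, NB 1: "NHL P53 status is based on central lab data". The next sentence reads: "If the central lab data is missing then the status will be considered Unknown". The list of Part 2 treatment groups in the same section then includes p53 Unknown NHL groups next to the mutant and wild-type ones.

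**What is collected.** Protocol 8.2.1: "For Part 2 NHL p53 status and NSCLC p53 WT status is required prior to dosing". The biopsy notes in that section add: "All NHL subjects in Part 2 must have a local p53 mutational analysis result prior to dosing". Tumors already shown to carry a p53 mutation are exempt, and archival or fresh tissue may be tested where local status was not determined. The revision chronology dates the local requirement to Amendment 6 (October 2020): "Inclusion of requirements for all NHL subjects in Part 2 to have local p53 mutational analysis done".

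**Model.** SAP 3.1.2, like protocol 11.4, says the hierarchical model "will be employed for the mTCC, TNBC, p53 WT NHL and p53 mutant NHL cohorts in Part 2". That makes four cohorts, two of them NHL.

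**Criterion.** SAP 2.4: "For NHL (p53 wild-type, p53 mutant, and p53 unknown cohorts), efficacy is defined as" a 30% response rate against a 10% historical rate. Protocol 11.1 sets the same rates for the wild-type and mutant cohorts only.

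**Declared changes.** SAP 2.1 states that nothing departs from the Amendment 8 analysis and then lists exceptions. One of them makes the p53 comparison in NHL a secondary analysis. Neither the central-only rule nor the Unknown criterion appears.

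**The concern.** Unknown p53 describes which data are available. It is not a disease population. Followed literally, NB 1 labels as Unknown a subject whose tumor has a documented p53 mutation, or a local wild-type result, whenever the central result is absent. That subject then leaves the wild-type versus mutant comparison, which the protocol synopsis names as a secondary goal of Part 2. Nothing says whether the subject contributes to either NHL cohort in the primary model.

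The Unknown group also acquires a success criterion of its own. Protocol Table 21 gives no operating characteristics for such a group, so a result judged against that criterion would have no known error rates. At stake are precision in the two NHL cohorts, a clean p53 comparison, and an undeclared third NHL efficacy claim.

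**Working it through.** **1. The texts side by side**

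| Question | Protocol | SAP |
|---|---|---|
| Number of NHL cohorts | Two (4.3.1, 11.1, 11.4) | Two in the model (3.1.2); three in the hypotheses and displays (2.4, 5.1.1) |
| Status needed before dosing | Yes (8.2.1) | Not used if the central result is missing (5.1.1) |
| Central result as an analysis rule | Stated for NSCLC (4.3.3.6). For NHL, central confirmation governs only further enrolment once the other NHL cohort reaches futility (8.2.1) | Applied to NHL (5.1.1) |
| Missing central value elsewhere | n/a | Baseline laboratory data fall back to the local value (5.2) |

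**2. Inputs for the size of the effect**

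- Maxima of 32 TNBC, 40 mTCC and 25 in each NHL cohort (protocol 4.3.3.2, Table 21).
- Futility below 0.15 and success at or above 0.87 (4.3.3.2, 11.9.6).
- First interim at 40 enrolled, then every 4 weeks; response known after 24 weeks (11.10.4.3).
- Appendix 11 model: treatment effect = logit(response rate) − logit(historical rate); Dirichlet process with α = 2; τ² ~ IG(3, 0.5) within a cluster. The spread of the μ prior is printed as 1.82. It was run as SD 1.8 and as variance 1.82 (SD 1.35), with similar NHL power. The figures below use SD 1.8.
- Assumed: uniform accrual over 104 weeks.

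The posterior is averaged over all 15 ways of grouping four cohorts. A grouping with k clusters of sizes n_c has prior weight 2^k × ∏(n_c − 1)! / (2·3·4·5).

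**3. Reproducing the plan's NHL figures at 25 per cohort (800 simulated trials per scenario)**

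| Quantity, NHL[+] / NHL[-] | Table 21 | Rebuilt |
|---|---|---|
| Power, All Positive | 0.95 / 0.96 | 0.955 / 0.962 |
| Power, 3 Null, 1 Positive (NHL[+]) | 0.81 | 0.808 |
| Type I error, All Null | 0.06 / 0.05 | 0.056 / 0.059 |

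The NHL figures reproduce. The match is looser elsewhere: mTCC type I error under All Null is 0.079 against a stated 0.10.

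**4. Removing Unknown subjects**

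The documents give no count of missing central results. Assumed losses per cohort of 25:

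- 12%: 25 − 3 = 22
- 20%: 25 − 5 = 20
- 32%: 25 − 8 = 17

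| n per NHL cohort | All Positive, NHL[+] / NHL[-] | 3 Null, 1 Positive, NHL[+] |
|---|---|---|
| 25 | 0.955 / 0.962 | 0.808 |
| 22 | 0.925 / 0.929 | 0.808 |
| 20 | 0.896 / 0.915 | 0.772 |
| 17 | 0.902 / 0.900 | 0.721 |

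Loss under All Positive: from 0.955 − 0.925 = 0.030 to 0.962 − 0.900 = 0.062. Loss under 3 Null, 1 Positive: from 0 to 0.808 − 0.721 = 0.087. The Monte Carlo standard error of a single entry is √(0.9 × 0.1 / 800) ≈ 0.011 near 0.90 and √(0.8 × 0.2 / 800) ≈ 0.014 near 0.80, so differences of a point or two between rows mean little.

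**5. Size of the Unknown group under the same assumption**

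2 × 3 = 6 to 2 × 8 = 16 subjects, set against a 30% versus 10% criterion.

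**The case against.** The best defence is that one central assay suits a comparison between genotypes. Protocol 4.3.3.6 itself foresees local and central p53 results disagreeing. Archival tissue is required from Part 2 subjects for retrospective testing that includes p53, and no protocol text says the local result defines NHL status for analysis. An openly labelled Unknown column is also transparent. This makes central-first reasonable. It does not justify discarding a documented mutation or local result when the central one is missing, and a central-only sensitivity table keeps the uniform-assay answer.

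Four stronger readings are tempting, and the documents do not support them:

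- *Every NHL subject has a local result.* The requirement dates from Amendment 6. New subjects started at 300 mg from Amendment 4, so those in the 400 mg Unknown group started under text that predates it. Known mutants are exempt. For some subjects there may be nothing to fall back on.
- *The SAP excludes Unknown subjects from the model.* This is an inference from the four-cohort definition. NB 1 sits under a display heading, SAP 1 leaves the hierarchical analysis outside the work of the organisation that wrote the SAP, and Unknown subjects remain in the All Treated NHL response displays. The plan is silent.
- *Central results are missing for reasons related to outcome.* This is possible, but neither document gives evidence for it.
- *Power collapses to about 0.70.* A stand-alone rule with a Beta(0.1, 0.9) prior gives 0.70 at 15 subjects, but it needs 4 responders at both 15 and 20. With Beta(0.5, 0.5) the cutoff at 15 drops to 3 and power is 0.87 (type I error 0.18). The figure reflects the cutoff, and it cannot be set beside Table 21, whose figures borrow across cohorts.

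**Conclusion.** The concern holds as a gap and an undeclared change that should be corrected before the final analysis. The SAP creates an Unknown NHL group by ignoring status information that the protocol asks for, gives that group an efficacy criterion absent from the protocol, and does not say how it relates to the four-cohort model.

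The effect on power is modest: about 3 to 6 points with all four cohorts active, and 0 to 9 points with one NHL cohort alone active. These figures assume that 12% to 32% per cohort are Unknown, that the cohorts would otherwise reach 25 (recruitment has stopped and the actual NHL numbers are not given), and that Unknown subjects stay out of the model. A local fallback recovers only those with a local result or documented mutation on record. The missing rule and the extra criterion need correcting whatever the count proves to be.

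**What to change.** In SAP 5.1.1, assign NHL p53 status in this order: central result; if missing, the local result or a previously documented p53 mutation; Unknown only when all are missing. In SAP 2.4, remove the 30% versus 10% criterion for Unknown and report that group descriptively. In SAP 3.1.2, state that Unknown subjects do not enter the p53-specific model cohorts. Add a table of NHL response by central status alone as a sensitivity analysis, with counts of subjects classified from each source. List the rule and the Unknown group among the departures in SAP 2.1.

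The cost is a few sentences and one table. The downside is some misclassification where local and central assays disagree, which the central-only table makes visible.

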5.1.2. PK Analysis: Handling of excluded data after NCA (Non-Compartmental Analysis) analysis

When Clinical Pharmacology perform the NCA analysis they may, in some circumstances, elect to exclude certain data points from the analysis. These data points should also be excluded from summary statistics. A separate analysis dataset ADPCWNL will be generated by adding a flag for those records to be excluded. PK listings and individual PK figures will keep all the data, with listings indicated the records excluded from summary.

5.2. Baseline Definitions

Baseline will be defined as the most recent, non-missing value prior to or on the first study treatment dose date for GSK3326595, including those from unscheduled visits.

For laboratory data, baseline will be defined as the most recent, non-missing value from a central laboratory prior to or on the first study treatment dose date. If there are no central labs collected for a subject and lab test prior to or on the first dose of study treatment, the most recent, non-missing value from a local laboratory prior to or on the first dose of study treatment will be defined as the baseline value.

If the latest pre-dose value is collected on the day of treatment, the time of treatment will be used to identify the baseline value. If time is not collected, Day 1 assessments are assumed to be taken prior to first dose and used as baseline.

Unless otherwise stated, if baseline data are missing, no derivation will be performed and baseline will be set to missing.

5.3. Multicenter Studies

As it is anticipated that accrual will be spread thinly across centers and summaries of data by center would be unlikely to be informative, data from all participating centers will be pooled prior to analysis.

5.4. Examination of Covariates, Other Strata and Subgroups

5.4.1. Covariates and Other Strata

There are no formal plans for any stratification. There are no formal plans for investigating any covariates.

5.4.2. Examination of Subgroups

There are no formal plans for examining subgroups.

